#### 10.4.1 GENERAL APPROACH

All tests will be two-tailed with the significance level set at 0.05. Analysis will be performed using STATA statistical software (StataCorp. 2015) or R (R: A language and environment for statistical computing. R Foundation for Statistical Computing, Vienna, Austria).

#### 10.4.2 ANALYSIS OF THE PRIMARY EFFICACY ENDPOINT(S)

##### **#1 (Primary): Quantify the impact of Shade on the cumulative number of new actinic keratoses developed over the study period.**

To test our primary aim, we will perform a control versus study group analysis. The study group will receive a Shade sensor and Shade app while the control group will standard of care sun avoidance counseling. The study will be randomized and single-blinded as described in section 10.6.1. This will also allow us to control for the effect of UV level variation on the primary outcome since the two groups will have balanced enrollment dates. All the patients will receive recommendations about UV exposure protection as defined by the recommendations of the American Academy of Dermatology and the National Cancer Institute.

Patients who will have used the Shade sensor for less than 15% of the days over the study period will be excluded from these analyses. We will use a Student's t-test with the following null and alternative hypothesis:

$$H_0: \text{mean}^C_{t12} (\text{AK}) = \text{mean}^I_{t12} (\text{AK})$$

$$H_a: \text{mean}^C_{t12} (\text{AK}) \neq \text{mean}^I_{t12} (\text{AK})$$

where  $\text{mean}^C_{t12} (\text{AK})$  is the averaged cumulative number of AK between enrollment follow up of controls and  $\text{mean}^I_{t12} (\text{AK})$  is the averaged cumulative number of AK of intervention patients.

In this analysis, demographic and clinical factors such as gender, age, baseline count of AKs, skin type, immunosuppressive treatment and comorbidity can be confounding factors. To test and control for confounding, demographic and clinical data (skin type, living area, gender, age, count of AK at enrollment, immunosuppressive (IS) treatment, level of immunosuppression and comorbidity) will be collected. We will use a stepwise multivariate approach with backward selection: 1) the effect of potential confounding factors will be tested using the same statistical tests, 2) factors with p-value <0.2 and less than 25% of missing values will be included in the multivariate model and 3) only covariates with significant adjusted p-value (<0.05) will be kept in the final model. Clinically relevant interactions will also be tested (e.g. skin type, gender, age) and kept in the final model if significant. The adjusted effect of Shade use will be estimated using a multivariate linear regression.

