control group will not wear a sensor. This choice of control group allows us to provide standard of care advice to these subjects. The behavior change in the treatment group is expected to be a result of both the decision to engage with the device, for example by putting it on and opening the App as well as due to the knowledge of personal UV exposure reported by the device. We expect to gather information on the cumulative UV exposure of all subjects by using an ELISA assay for cyclopyridimine dimers (CPD) from photoexposed skin.

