### 5.2 PARTICIPANT EXCLUSION CRITERIA

1. Has received UV therapy in the past 6 months.
2. Has had field therapy (e.g., entire face or scalp) for the treatment of actinic keratosis (e.g. topical imiquimod, 5-fluorouracil, photodynamic therapy) in the past 3 months.
3. Patient's work and or their lifestyle is not compatible with wearing a UV sensor.
4. Has difficulty controlling their own UV exposure (nursing home, long term hospitalization).
5. Has a medical condition judged incompatible with the study by the enrolling physician including the presence of an ICD or an existing plan for an extended inpatient treatment.
6. Is an employee or direct relative of an employee of the investigational site or study sponsor.
7. Must have a smartphone that is compatible with the Shade app and is comfortable using a new app (the Shade app) on their smartphone.
  - a. Jitterbug and the Samsung Galaxy J3 are not compatible with the app

Ongoing exclusion criteria:

If subject is not able to meet the commitment to ongoing visits or their answer to the exclusion criteria questions changes the subject will be removed from the study. If the change in status is temporary, less than three months, the decision to remove a subject from the study will be at the discretion of the PI.

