#### 10.4.3 ANALYSIS OF THE SECONDARY ENDPOINT(S)

##### **#2 (Secondary): Quantify the impact of Shade on the numbers of new AK's observed at the final visit**

This analysis will follow the same procedure as the primary analysis but will only include AK data from the final visit.

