We will also quantify the percentage of observant and non observant patients, as well as the percentage of responsive and non-responsive patients. While observance will be based on the use of the sensor, responsiveness will be based on "safe" UV behaviors. Observance will be defined as at least 50% of days used, poor observance between 15% to 50% and non-observance as inferior to 15%. Responsiveness will be defined as less than 15% days over the UV threshold and more than 85% of days with an UV threshold set within one standard deviation of the study group's average UV threshold. Conversely, non-responsiveness is defined as more than 15% days over the UV threshold or more than 85% of days with an UV threshold set above one standard deviation of the study group's average UV threshold.

The sociodemographic and clinical characteristics of observant, poorly observant, non-observant, responsive and non-responsive patients will be assessed separately and compared using Student's t-tests for quantitative characteristics and  $\chi^2$  for categorical characteristics. These comparisons will provide useful information to better understand the determinants of UV behaviour change.

To be conservative, only non-observant subjects (<15% of days use) will be excluded from the analyses while poorly and non-responsive patients will be included. The comparison of their characteristics will rule out a selection bias.

**#10 (Secondary): Assess feasibility of the intervention for kidney transplant recipients through report of their rates for compliance and retention.**

Rates will be reported but are not expected to be analyzed for significance.

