## 10.4.10 TABULATION OF INDIVIDUAL RESPONSE DATA

Clinical data tables will be reduced into a table of individual responses for analysis as follows:

Column	Source (name of CRF with data)
SubjectID	N/A
AK baseline (count)	Actinic Keratosis
AK follow up (cumulative count)	Actinic Keratosis
NMSC baseline (count)	NMSC
NMSC follow up (cumulative count)	NMSC
Observant % of days	Compliance database
Responsive Y/N	Shade database: days with UV limit below 90% of exposures
CPD R 0	Lab data
CPD R 12 month	Lab data
MHA 1	PROMIS MHA visit 1
MHA 2	PROMIS MHA visit 2
MHA 3	PROMIS MHA visit 3
MHD 1	PROMIS MHD
MHD 2	PROMIS MHD
MHD 3	PROMIS MHD
SHP 1	PROMIS SHP
SHP 2	PROMIS SHP
SHP 3	PROMIS SHP
UV Ave	Sensor data
AE (count)	CRF
comment	

group	Randomization
exclude	

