### 10.5 SAMPLE SIZE

The most efficient approach to performing the power calculation for this study via Monte Carlo simulation as the underlying phenomenon, AK rate, is best modeled by a Poisson distribution.

As a starting point, we took the distribution of AK rates from actual clinical data. The data were assembled by querying EPIC on 2014 visits of kidney transplant patients to dermatology (this subset of the population will have fewer AK's than the non-transplant subjects and therefore use of this distribution will err on the side of caution toward overpowered the study). For each visit in which the dermatologist chose to treat by LN2 destruction, the query retrieved the number of procedures performed. This approach is conservative as the input data potentially underestimates AK count as some AK's may not have been treated.

The structure of the Monte Carlo was straightforward. A set of potential study sizes (N recruited) and effect sizes were chosen. For each input condition, two thousand random experiments were performed. In each of these interactions, baseline AK rates were drawn from the clinically observed distribution of AK's. Subjects were sequentially assigned to treatment or control groups. Observed AK rates were generated using a Poisson distribution for each visit. The analysis expected for the study was then performed. In this analysis the total count of AK's for each subject was obtained and the means and distributions compared for directionality (AK\_treated < AK\_control) and significance (p-value from a one-tailed t-test).

Analysis was performed in R (R Open 3.2.3) with statistical calculations and random number generation using the base and stat libraries.

[figure not shown]

Figure 10.5.1. With an effect size of 0.25 and recruitment of 100 patients (50 treatment, 50 control) we predict a power of 0.81.

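### The primary analysis drops low sensor users, which can only happen in the study arm, so it no longer compares the groups that were randomised

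*Combined protocol and SAP*

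**What the plan says.** Section 10.4.2 states, immediately before the primary t-test, that patients who "used the Shade sensor for less than 15% of the days over the study period will be excluded from these analyses". Endpoint #9 in section 10.4.3 repeats the rule in general terms, "only non-observant subjects (<15% of days use) will be excluded from the analyses", and calls it conservative because poor users (15% to 50% of days) and non-responsive patients are kept. It adds: "The comparison of their characteristics will rule out a selection bias". Endpoint #2 inherits the rule: "This analysis will follow the same procedure as the primary analysis but will only include AK data from the final visit".

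Section 2.2 says that the "control group will not wear a sensor", and section 10.6.1 gives controls counselling only. Section 10.3 covers data preparation and defines no analysis set. No section describes an analysis of everyone randomised.

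The table in section 10.4.10 lists AK counts, "Observant % of days", group and an exclusion column. The power simulation in section 10.5 is described as one in which "the total count of AK's for each subject was obtained and the means and distributions compared for directionality"; it mentions no exclusion for non-use.

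**The concern.** Taken literally, the rule would remove every control, since none of them uses a sensor. It can only work as a filter on the study arm. That filter depends on what patients do after randomisation, and the controls have no matching one. Those controls who would not have worn a sensor remain in the comparison, while their study-arm counterparts leave.

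People who stop wearing a UV sensor may also differ in sun behaviour or AK risk. If so, the two means differ even when the device does nothing, and the primary test need not hold its stated error rate. A significant AK reduction could then partly reflect who kept wearing the sensor. Section 3 says that the data will support the indications for use, so this matters for the main claim of the trial.

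**Working it through.** **Inputs from the documents.** 120 patients allocated 1:1, so 60 per arm (section 4.1). Student's t-test (10.4.2), two-sided at 0.05 (10.4.1). Power 0.81 for a 25% reduction with 50 per arm, one-tailed (10.5).

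**Inputs not in the documents, assumed here.** q is the share of patients who are or would be non-users; k is their AK rate relative to users. Follow-up is complete and the users' mean count is 8.

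**The plan's own power figure.** The AK distribution is not given, so 0.81 can be neither confirmed nor refuted, but it can be used to find the variability it implies. Set the control mean to 1 and assume one-sided alpha 0.05, which section 10.5 does not state. With equal SDs s, the noncentrality is 0.25 / (s√(2/50)). At s = 0.49 this is 0.25 / 0.098 = 2.55, against a critical value of 1.66, giving 0.81. If the treated SD shrinks with the mean, the control CV (SD divided by mean) that gives 0.81 is 0.56. I used 0.56 for the bias simulations and 1.0 as a more variable case.

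**Spurious reduction.** With no device effect, the control mean relative to users is 1 − q + qk, and the retained study arm has mean 1. The apparent reduction is 1 − 1/(1 − q + qk). For q = 20%, k = 1.5: 1 − 1/1.10 = 9.1%.

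**False wins for Shade (nominal 2.5%).** 40,000 simulated gamma-Poisson trials per row, pooled t-test, low users dropped from the study arm only:

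| q | k | Apparent reduction | CV 0.56 | CV 1.0 |
|---|---|---|---|---|
| 5% | 1.25 | 1% | 3% | 3% |
| 5% | 1.5 | 2% | 4% | 3% |
| 10% | 1.25 | 2% | 4% | 3% |
| 10% | 1.5 | 5% | 6% | 4% |
| 20% | 1.5 | 9% | 13% | 6% |
| 20% | 2 | 17% | about 40% | 13% |
| 20% | 1 | none | 2.4% | 2.4% |
| 20% | 0.75 | 5% increase | under 1% | about 1% |

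Analysing everyone as randomised gives about 2.5% in every row.

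**Does covariate adjustment rescue it?** Linear regression on group and baseline AK count, CV 0.56, 20,000 trials per scenario:

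| q | k | Excess already present at baseline | Excess arises only in follow-up |
|---|---|---|---|
| 5% | 1.25 | 3% | 3% |
| 10% | 1.5 | 4% | 8% |
| 20% | 1.5 | 6% | 17% |
| 20% | 2 | 12% | 46% |

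Adjustment helps when baseline counts already show the difference. It does not help when the difference lies in later behaviour.

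**The case against.** The strongest reply is that the excluded group may be tiny. The 15% cut-off is low. Section 5.2 screens out people whose "lifestyle is not compatible with wearing a UV sensor", section 5.3 pays for use on more than 40% of days, and section 7.3.3 offers coordinator support. At 5% non-use the inflation is small, and the 40% row is an extreme corner: holding the whole-arm CV at 0.56 with k = 2 forces the users' own spread down, and at CV 1.0 the figure is 13%. The trial also recruits 120 against the 100 simulated. At 20% non-use, 48 study-arm patients would remain, close to the 50 assumed.

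All of this stands as a limit on likely size. None of it restores the randomised comparison. The plan states no expected rate of non-use, and it does not say that the recruitment margin is for non-users. A margin in numbers protects power and does nothing about bias.

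The plan's own defence does not stand. Comparing measured characteristics between users and non-users cannot exclude differences in unmeasured sun behaviour, and with few non-users it would detect little. Nor is the rule conservative in the statistical sense, because it can favour Shade.

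**Conclusion.** The concern holds and should be fixed before the blind is broken. The rule is a post-randomisation exclusion that only one arm can trigger, it governs the primary test and endpoint #2, and no all-randomised analysis stands beside it. This conclusion follows from the text and needs no assumption.

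The size does need assumptions. The bias is negligible at around 5% non-use with a modest risk difference, material at 20% non-use with k of 1.5 or more, zero if expected counts are equal, and against Shade if non-users have fewer AKs. The documents give neither the rate of non-use nor the AK risk of non-users, so the direction is unknown.

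**What to change.** - In section 10.4.2 and endpoint #9, replace the exclusion with a statement that all randomised patients with AK follow-up are analysed in their assigned group, regardless of sensor use. Endpoint #2 then follows.
- Keep the 15% rule only as a labelled supportive (per-protocol) analysis.
- Delete the claim that comparing characteristics settles selection bias.
- In section 10.5, restate two-sided power for the all-randomised analysis with an assumed rate of non-use.

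No visit or measurement is added; the section 10.4.10 table already holds what is needed. The cost is dilution. Suppose non-users gain nothing, the effect in users is 25%, and both SDs are 0.49 of the control mean. The planned exclusion compares 60 controls with 60(1 − q) study patients at effect 0.25; the all-randomised analysis compares 60 with 60 at effect 0.25(1 − q). Two-sided power is then:

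| Non-users | Planned exclusion | All randomised | Per arm to match |
|---|---|---|---|
| 5% | 0.78 (60 v 57) | 0.75 | 65 |
| 10% | 0.77 (60 v 54) | 0.70 | 70 |
| 20% | 0.74 (60 v 48) | 0.60 | 83 |

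The sponsor should either state the lower power or revisit the sample size.

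The change removes the sensor-use filter only. Missing follow-up, and the ongoing removals in section 5.2 (one of whose criteria concerns compatibility with wearing a sensor and may in practice fall mainly on the study arm), need separate attention.

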##### **#3 (Secondary): Quantify the impact of Shade on the numbers of new cutaneous squamous cell carcinomas confirmed by histology during follow up over the study period.**

To test the early effect of Shade on skin cancer risk and the robustness of our findings, we will perform a longitudinal analysis to test a reduction by at least 25% of squamous cell carcinoma. The effect of Shade use will be estimated using a single mixed linear model (with random intercept and slope) for repeated (longitudinal) data including study group and time since enrollment as explanatory variables. A similar stepwise multivariate approach with backward selection as described in the primary aim will be performed to take into account confounding factors.

**#4 (Secondary): Quantify the impact of Shade on the number of new nonmelanoma skin cancers (basal cell carcinomas, cutaneous squamous cell carcinomas) confirmed by histology over the study period.**

To test the early effect of Shade on skin cancer risk and the robustness of our findings, we will compare the cumulative numbers of new nonmelanoma skin cancers between the control and study group and test a reduction by at least 25% of non-melanoma skin cancer s as secondary outcome, using a t-test. A similar stepwise multivariate approach with backward selection as described in the primary aim will be perform to take into account confounding factors.

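### The primary t-test uses neither the baseline AK count nor the Fitzpatrick randomisation stratum, and although it reads as the deciding analysis, no section labels it so

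*Combined protocol and SAP*

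**What the plan says.** Section 10.4.2 introduces the primary test with "We will use a Student's t-test with the following null and alternative hypothesis", and the hypotheses that follow compare the mean cumulative AK counts of the two arms. Neither the hypotheses nor the test contains a covariate. Section 10.4.1 sets the level: "All tests will be two-tailed with the significance level set at 0.05".

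Section 10.4.2 then lists factors to be collected as possible confounders: "skin type, living area, gender, age, count of AK at enrollment, immunosuppressive (IS) treatment, level of immunosuppression and comorbidity". A factor enters the multivariable model if its own p-value is below 0.2 and fewer than 25% of its values are missing. After backward selection, "only covariates with significant adjusted p-value (<0.05) will be kept in the final model". The paragraph ends: "The adjusted effect of Shade use will be estimated using a multivariate linear regression". Baseline AK count and skin type are therefore candidates, but neither is certain to stay in the model.

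Sections 4.1 and 10.6.1 provide separate randomisation lists for Fitzpatrick I-II and for III and above. Section 10.4 defines success as a significant reduction of at least 25% without saying which analysis supplies it. Section 10.5 describes the simulated power analysis with "The analysis expected for the study was then performed", and what was simulated is a t-test on total counts.

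In section 10.4.3, aim #2 repeats the arrangement: "This analysis will follow the same procedure as the primary analysis but will only include AK data from the final visit". Aim #4 uses a t-test and then adds: "A similar stepwise multivariate approach with backward selection as described in the primary aim will be perform to take into account confounding factors".

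**The concern.** Two things are at stake.

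The first is precision. A patient's AK count at enrolment may well predict the count of new lesions later, and the plan itself names it as a factor that can affect the comparison. If the t-test decides, any such information goes unused in the result that matters. The randomisation stratum is also left out, although a factor used to allocate patients is normally carried into the primary model.

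The second is clarity. The plan produces two estimates of the same effect, one unadjusted and one adjusted, and does not rank them in words. They can disagree on significance, so the label should be fixed before anyone sees results by arm.

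**Working it through.** **The plan's own figure.** Section 10.5 gives power 0.81 with 50 per arm, a 25% reduction and a one-tailed t-test. The AK distribution behind it is not in the documents, so the figure cannot be reproduced independently. It can only be solved backwards for the implied CV (SD divided by mean). One-tailed alpha is taken as 0.05.

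- If SD scales with the mean, the standard error relative to the control mean is CV × √[(1 + 0.75²)/n]. Power 0.81 at n = 50 implies CV of about 0.56.
- If both arms have the same SD, it implies CV of about 0.49.

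I use CV 0.57 with SD scaling with the mean. This is slightly more cautious than the implied 0.56: it gives 0.79 for the plan's own one-tailed case.

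**Inputs.** From the documents: 120 patients, 60 per arm (4.1); 25% reduction (10.4, 10.5); two-sided 0.05 (10.4.1). Assumed: CV 0.57, correlation r between baseline and follow-up counts, and all 120 patients analysed.

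**Unadjusted t-test.** Standard error = 0.57 × √(1.5625/60) = 0.0920. Noncentrality = 0.25/0.0920 = 2.72. With 118 degrees of freedom, power = **0.77**.

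**Baseline count always included.** The standard error is multiplied by √(1 − r²), which is equivalent to 60/(1 − r²) patients per arm. The degree of freedom spent on the covariate is ignored.

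| r | √(1 − r²) | Noncentrality | Power | Equivalent n per arm |
|---|---|---|---|---|
| 0 | 1.000 | 2.72 | 0.77 | 60 |
| 0.15 | 0.989 | 2.75 | 0.78 | 61 |
| 0.35 | 0.937 | 2.90 | 0.82 | 68 |
| 0.55 | 0.835 | 3.25 | 0.90 | 86 |

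**Other CVs**, in the order r = 0, 0.15, 0.35, 0.55:
- CV 0.5: 0.87, 0.87, 0.91, 0.96
- CV 0.7: 0.59, 0.60, 0.65, 0.75
- CV 0.9: 0.40, 0.41, 0.45, 0.53

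**Simulation check.** Patient rates were gamma distributed with within-person drift (CV 0.3) in both periods. Counts were Poisson, total control CV was 0.57, and the baseline mean was half the follow-up total. There were 60 per arm, a stratum effect of zero, and 3,000 trials per scenario (Monte Carlo SE about 0.008).

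| Control mean total AKs | r | t-test | Baseline and stratum forced in | Stepwise, screened on outcome |
|---|---|---|---|---|
| 6 | 0.15 | 0.74 | 0.74 | 0.74 |
| 10 | 0.33 | 0.76 | 0.80 | 0.81 |
| 20 | 0.49 | 0.76 | 0.85 | 0.86 |

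At control means of 4.5 and 5, r was 0.02 and 0.08 and there was no gain (0.75 vs 0.75, and 0.75 vs 0.74). With 100 patients analysed, the three means gave 0.67, 0.67 and 0.69 for the t-test against 0.66, 0.71 and 0.80 with forced covariates.

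**Type I error, all randomised patients analysed.** Across the simulated settings (4,000 null trials each, SE about 0.0035), the t-test gave 0.046-0.051, the forced model 0.044-0.053 and the selected model 0.047-0.055. Taking the more favourable of the t-test and the selected model would give 0.058-0.074.

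**How often the label matters.** In a separate run of the same design with a true 25% effect, the t-test and the selected model disagreed on significance in 4%, 10% and 12% of trials at means 6, 10 and 20.

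**The case against.** The strongest reply is that the plan already has an ordinary structure: a main test followed by a supportive adjusted estimate. The hypotheses are written for the t-test, the power simulation uses a t-test, and the regression is introduced only to deal with confounding. This largely stands. The t-test is the natural deciding analysis, and what is missing is an explicit label.

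It is also fair that the power gain rests on inputs nobody outside the study team can see. Section 5.1 admits patients with a single AK diagnosis in the past year, so low counts and a low r are plausible. The gain could then be nil.

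A reader might go further in four ways that the documents do not support:

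- *That the plan inflates type I error to about 0.06-0.07.* This would happen only if the more favourable of the two results were reported, and no section proposes that.
- *That p-value selection itself loses power.* If factors are screened against the outcome, which is the natural reading, the selected model performs like the forced one.
- *That leaving out the stratum costs power.* The simulations set its effect to zero and show nothing either way.
- *That the adjusted analysis cannot be run because the table in 10.4.10 lacks most of the covariates.* Section 10.3 lets the statistician request the table format, and sections 10.4.6 and 14.4 provide for demographics, skin type and transplant status. The table is at most incomplete.

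Nor should the t-test, as planned, be called unbiased. Section 10.4.2 excludes patients with sensor use on fewer than 15% of days, which can remove only study-arm patients because controls wear no sensor. That is a separate problem. Adjusting for baseline and stratum does not repair it, and the error rates above assume that nobody is excluded.

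**Conclusion.** The point holds in a limited form. The primary test leaves out a collected baseline measure of the outcome and the factor used to stratify randomisation. The text leans clearly to the t-test as the deciding analysis but does not label it, or the adjusted effect, as such.

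The likely cost is precision. At CV 0.57 and 60 per arm the gain from including baseline is about 1 percentage point of power at r = 0.15, 5 at r = 0.35 and 13 at r = 0.55. Neither CV nor r is in the documents, so the gain may be near zero. The simulations show no meaningful loss of power from always including the two covariates. The benefit that does not depend on r is a single named primary result. The change is worth making, but nothing here shows that the planned test has the wrong error rate.

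**What to change.** In section 10.4.2, name one primary analysis: linear regression of cumulative new AKs on arm, baseline AK count and Fitzpatrick stratum (I-II vs III-VI). Keep both covariates in regardless of their p-values, and report the arm coefficient with its 95% confidence interval. This still estimates a difference in means, so the stated hypotheses need only be read as adjusted for the two covariates.

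Label the t-test and the stepwise model as sensitivity analyses, state that screening is against the outcome, and label the interactions as exploratory. Say in section 10.4 that the success criterion is judged on the named analysis. Apply the same model to aim #2, and name one deciding analysis for aim #4.

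The cost is wording plus a request under section 10.3 that the analysis dataset carry skin type. No new patient data are needed: section 10.4.2 already collects both covariates, and section 7.3.2 records skin type at enrolment. Section 17.2 shows that some subjects had completed visit 2 when the protocol was last changed, so this should be a dated amendment made before the unblinding in section 10.6.3. The sensor-use exclusion needs its own correction.
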